#### 2.4 Substudies

#### **Serum for Banking**

As a substudy of the CAMUS trial, participant's serum will be stored on a voluntary basis in the Central Repository of the NIDDK located in Germantown, Maryland. The purpose of this serum bank is to allow future studies specific to BPH progression in this population. Specific ancillary studies will be guided by the study outcomes. No genetic analyses will be performed. Because the samples are stored in the NIDDK Central Repository, investigators unrelated to this trial may eventually have access to these samples in accordance with NIDDK policies.

Serum samples will be obtained from participants after giving proper consent specific for blood storage and maintaining a database for future research. A maximum of 2 samples will be obtained. The first will be obtained at screening visit #1 and the second at the conclusion of the trial (72 week visit).

The participant's health care information will be maintained in an anonymous database maintained by the Data Coordinating Center. It will be provided to the Central Repository after the database has been locked. Both the serum samples and database will

be stripped of all identifiers so that the participant's confidentiality will be maintained. The details of serum banking and confidentiality are located in the Manual of Operations.

Studies using the serum samples will be performed in accordance with NIH Policy.

#### 3.0 PATIENT SELECTION

#### 3.1 Eligibility Criteria

To be eligible for the study, potential participants must meet all of the following eligibility criteria:

- 1. Male at least 45 years of age.
- 2. Peak urinary flow rate at least 4 ml/sec with a voided volume of at least 125 ml.
- 3. AUA symptom score  $\geq 8$  and  $\leq 24$  at both screening visits.
- 4. Voluntarily signed informed consent agreement prior to the performance of any study procedures.

#### 3.2 Exclusion Criteria

Potential participants that meet any of the following exclusion criteria will be excluded from the full-scale trial:

- 1. Any prior invasive intervention for BPH.
- 2. Phytotherapy for BPH or a 5-alpha reductase inhibitor within 3 months.
- 3. Alpha blocker within one month.
- 4. Reported allergic reaction to Serenoa Repens.
- 5. Taken an oral alpha agonist, tricyclic antidepressants, and anticholinergic or cholinergic medication within 4 weeks of the first screening visit, with the following exception: topical anticholinergic eye drops used for glaucoma or inhaled anti-cholinergic used for COPD.
- 6. Taken an estrogen, androgen, or any drug producing androgen suppression, or anabolic steroids within 3 months.
- 7. Known clinically significant renal impairment (i.e., creatinine greater than 2.0 mg/dl).

- 8. ALT (SGPT), AST (SGOT) or GGT value greater than 3 times the upper limit of normal in the clinical center lab at SV1.0; confirmed on a second measurement.
- Prothrombin time greater than 3 seconds above the upper limit of normal, or more than 3 seconds above the control value in the clinical center at SV1.0; confirmed on a second measurement.
- 10. ECG reading at the clinical center at SV1.0 or SV2.0 suggesting active ischemia or recent myocardial infarction until appropriate consultation confirms the absence of an acute coronary syndrome.
- 11. PSA level greater than 10 ng/ml at the first screening visit.
- 12. Requires the daily use of a pad or device for incontinence, or ICS*male*IS score >14 at screening.
- 13. Unstable medical condition within the past 3 months.
- 14. History or current evidence of carcinoma of the prostate, pelvic radiation, urethral stricture, or prior surgery for bladder neck obstruction.
- 15. Active urinary tract disease or has undergone cystoscopy or biopsy of the prostate within one month prior to the first screening visit or has an imminent need for urologic surgery.
- 16. Known primary neurologic conditions such as multiple sclerosis or Parkinson's disease or other neurological diseases known to affect bladder function.
- 17. Documented bacterial prostatitis within the past year.
- 18. Two documented independent urinary tract infections of any type in the past year.
- 19. Known severe bleeding disorder or need for ongoing therapeutic anticoagulation with Coumadin, Heparin, or Plavix.
- 20. Cancer, which is not considered, cured (except basal cell or squamous cell carcinoma of the skin). Men with a prior diagnosis of cancer are excluded unless the principal investigator at the site considers the individual cured or at low risk of recurrence. In general 5 years from the diagnosis of the cancer should have elapsed without recurrence to be considered cured or at low risk

of recurrence. The exception is for basal cell or squamous cell skin cancers. Men with a history of prostate cancer regardless of curability are not eligible.

- 21. Unable to follow protocol directions due to organic brain or psychiatric disease.
- 22. History of alcoholism or any other substance abuse, which, in the opinion of the investigator, would affect compliance with the protocol.
- 23. Any serious medical condition likely to impede successful completion of the study.
- 24. New diuretic prescription or change in diuretic dose within the last month.

#### 3.3 Randomization and Stratification

Following a successful screening period, the participant will be officially randomized to one of the two treatment groups:

- Serenoa Repens
- Placebo

This study will use a stratified randomization scheme with equal numbers of participants in each treatment group. Stratification will be by clinical center and AUA Symptom Score (8-15; 16-24). Within each stratum, the method of randomly permuted blocks will be used to ensure that an equal number of participants are assigned to each treatment group.

Clinical Centers will randomize participants to treatment groups using a centralized, data-based system. Password protection will be implemented to ensure that only certified clinical center personnel are allowed to randomize patients. At the time of randomization, each participant will be assigned a unique medication kit identification number that will be used throughout the duration of the study.

#### 4.0 TESTS AND OBSERVATION

See Schedule of Evaluations - Appendix I

#### 4.1 Informed Consent

Prior to screening visit #1 (SV1.0), potential participants will undergo pre-screening procedures (e.g., chart review, telephone interview) to identify candidates for screening visits; this pre-screening is identified as SV0.0. If a potential participant is identified during SV0.0, then SV1.0 will be scheduled. During SV1.0, the trial and procedures will be thoroughly explained and the participant will be asked to sign an informed consent form. The informed consent form developed by the Steering Committee will be used as a model (see Appendix III). Each center will develop its own modification of the consent form based on the requirements of its own institutional review board.

#### 4.1.1 Screening Visit #1 (SV1.0)

During Screening Visit #1, after the participant has signed the informed consent document, the participant will undergo the following procedures to determine eligibility:

#### 4.1.1.1 Medical History, including:

- History of urinary retention, gross hematuria and microscopic hematuria
- Prior biopsy of the prostate
- Family history of BPH
- Family history of prostate cancer
- Date of vasectomy, if applicable
- History of sexual dysfunction or incontinence
- History of BPH symptoms
- Demographics and social characteristics

#### 4.1.1.2 Physical Exam, including (could be done at SV2.0)

- Vital signs (pulse rate and blood pressure)
- Height and weight
- Digital rectal examination

#### 4.1.1.3 Assessment of all medications

#### 4.1.1.4 Laboratory Tests

- Prostate Specific Antigen (PSA). The PSA measurements will be determined by a central laboratory. Please refer to the manual of operations, Chapter 7, for specimen collection and shipping instructions.
- Urinalysis, including dipstick. If dipstick is positive (greater than 0) for blood or leukocyte esterase, a specimen will be sent for microscopic analysis.
- Complete blood count (CBC), prothrombin time (PT) and serum chemistry profile: serum creatinine, sodium, potassium, chloride, glucose, bicarbonate, ALT (SGPT), AST (SGOT) and GGT.
- Serum for Banking
- 12-lead electrocardiogram (with a copy of the tracing and interpretation stored in the participant's study record). Can be performed at SV1.0 or SV2.0.

#### 4.1.1.5 Urinary Function:

- Uroflow measurement to include: voiding time, flow time, time to maximum flow, peak flow rate, mean flow rate, voided volume and post void residual (PVR).
- 4.1.1.6 International Prostate Symptom Score (IPSS). Note: IPSS=AUA Symptom Score plus IPSS Quality of Life question.

#### 4.1.2 Screening Visit #2 (SV2.0)

If the participant successfully satisfies the inclusion/exclusion criteria based on the measurements during SV1.0, he will be scheduled for screening visit #2 (SV2.0). During SV2.0, the following procedures will be performed:

- 4.1.2.0. Physical Exam, including (could be done at SV1.0)
  - Vital signs (pulse rate and blood pressure)
  - Height and weight
  - Digital rectal examination
- 4.1.2.1 Uroflow measurement to include: voiding time, flow time, time to maximum flow, peak flow rate, mean flow rate, voided volume and post void residual (PVR).
- 4.1.2.2 IPSS (this value will be considered the participant's baseline value).
- 4.1.2.3 BPH Impact Index
- 4.1.2.4 Bladder Function (this value of the ICS*male*IS will be considered the participant's baseline value).
- 4.1.2.5 Vital signs (pulse rate and blood pressure).
- 4.1.2.6 12-lead electrocardiogram (with a copy of the tracing and interpretation stored in the participant's study record). Note: test at SV2.0 if this was not obtained in SV1.0.

The screening process ends with either documentation of participant ineligibility and dismissal or documentation of participant eligibility and randomization.

#### 4.2 Randomization and Baseline Evaluation

Randomization can be combined with screening visit #2 for the participant's convenience.

- 4.2.1 Eligibility determination and Randomization.
- 4.2.2 Provision of assigned study medications.

4.2.3 Baseline questionnaires: Jenkins Sleep Dysfunction Scale, Erectile Function, Ejaculatory Function, NIH- Chronic Prostatitis Symptom Index (CPSI).

#### 4.3 Evaluations during Treatment and Follow-Up

- 4.3.1 Focused physical examination (including height and weight) and digital rectal examination at the 72 week visit.
- 4.3.2 Medical follow-up to include new diagnoses, treatments, hospitalizations, life events at the 4, 12, 24, 28, 36, 48, 52, 60 and 72 week visits.
- 4.3.3 Hematology: CBC and PT at the 12, 24, 36, 48, 60 and 72 week visits.
- 4.3.4 Serum chemistries: serum creatinine sodium, potassium, chloride, bicarbonate, glucose, ALT (SGPT), AST (SGOT) and GGT at the 12, 24, 36, 48, 60 and 72 week visits.
- 4.3.5 Urinalysis, including dipstick at the 72-week visit. If dipstick is positive (greater than 0) for blood or leukocyte esterase, then a specimen will be sent for microscopic analysis.
- 4.3.6 PSA at the 24, 48, and 72 week visits. The PSA measurements will be determined by a central laboratory. Please refer to the Manual of Operations for specimen collection and shipping instructions.
- 4.3.7 Vital signs at the 4, 12, 24, 28, 36, 48, 52, 60 and 72 week visits. (Visits 4, 28 and 52 can be optional phone interviews. A blood pressure monitor will be provided to participants to record blood pressure at home. The participant must agree to give 2 sitting readings to the study personnel.)
- 4.3.8 Uroflow measurement to include: voiding time, flow time, time to maximum flow, peak flow rate, mean flow rate, voided volume and post void residual at the 12, 24, 36, 48, 60 and 72 week visits.

- 4.3.9 Bladder Function, IPSS (AUA Symptom Score plus IPSS Quality of Life questions), and BPH Impact Index questionnaires, at the 12, 24, 36, 48, 60 and 72 week visits.
- 4.3.10 Erectile Function, Ejaculatory Function, NIH-CPSI, Jenkins Sleep Dysfunction Scale and Subjective Global Assessment, and participants' perception about whether they are on active therapy or placebo at the 24, 48, and 72 week visits.
- 4.3.11 Treatment compliance by pill count and provision of assigned study medication at the 12, 24, 36, 48, 60, and 72 week visits.
- 4.3.12 Adverse event assessment at the 4, 12, 24, 28, 36, 48, 52, 60, and 72 week visits.
- 4.3.13 Assessment of all medications, including over-the-counter medications, at the 4, 12, 24, 28, 36, 48, 52, 60 and 72 week visits, or when and adverse event occurs. (Visits 4, 28, and 52 can be omitted if optional phone interview chosen.)
- 4.3.14 Serum for banking at SV1.0 and 72 week visit.
- 4.3.15 12-lead electrocardiogram (with a copy of the tracing and interpretation stored in the participant's study record) at 24, 48 and 72 weeks visit.

Optional phone interview or office visit at 4, 28 and 52 weeks. A participant has the option of either an office visit or phone interview for visits 4, 28 and 52. Medical follow-up, height, weight and medications review will not be required if phone interview for weeks 4, 28 and 52 only. Still assess any AE if necessary (inquiry). All forms required at the visits will have to be completed during the interview. A blood pressure monitoring device will be provided to the participant to satisfy the BP requirement.

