#### 5.9 Criteria for Study Discontinuation

All participants should be followed for 72 weeks from the date of randomization, and should be encouraged to undergo all protocol procedures. Participants may withdraw from the study at any time.

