#### 8.0 STATISTICAL CONSIDERATIONS

#### 8.1 Sample size estimation

The primary goal of this study is to determine the efficacy and safety profile of treatment with *Serenoa Repens* compared to placebo. The primary end point of the study is change in AUA symptom score from baseline to 72 weeks. The sample size estimate is based on the following assumptions: a difference in the change in the AUA symptom score from baseline to 72 weeks of 2 points between the placebo arm and the phytotherapy arm, a common standard deviation of the AUA symptom score of 6 points, a two-group t- test, a one-sided significance level of 0.05 and a statistical power of 90%. A one-sided statistical test will be used since an improvement in the AUA symptom score with therapy (i.e., efficacy of therapy) is of primary interest. To detect the hypothesized difference in the change in the AUA symptom score, a sample size of 157 participants per arm will be required. Therefore, a total of 314 participants will be required for the study. To allow for a 10% dropout rate over the course of the study, 350 participants will be recruited to the study.

To determine the power for evaluating safety by measuring hematology and serum chemistry levels, it is assumed that the underlying probability of a severe or life-threatening adverse event detected by laboratory results for placebo is < 2.5%. With 157 participants in each treatment arm, the power to detect a severe or life-threatening adverse event that occurs with frequency  $\ge 10\%$  in the phytotherapy arm at the one-sided 0.05 significance level is 80%.

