APPENDIX I - Schedule of Evaluations (Screening Visit 1 - Week 24)

		Screenii	ng Visits				
	PROCEDURE	1	2 (2)	Baseline (2)	Week 4 (7)	Week 12	Week 24
FORM	Informed Consent	X					
CAM01	Eligibility & Randomization			X			
CAM21	Medical History	Х					
CAM22	Medical Follow-Up				Χ	Χ	Х
CAM23/24	Assessment of all medications (1)	Х		X	Χ	Χ	X
CAM31	Vital Signs	Х	Х		Χ	Χ	X
CAM32	Physical & Digital Rectal Exam	X (8)	X (8)				
CAM41	PSA	Х					X
CAM42	Uroflow Measurement	Х	Х			Χ	Х
CAM45	Hematology: CBC/PT/Serum Chemistries	X				Χ	Х
CAM46	Urinalysis	Х					
CAM47	Serum for Banking (3)	Х					
CAM48	EKG (6)	X (6)	X (6)				Х
CAM51	Study Drug Administration & Compliance					Χ	X
CAM61	BPH Outcome Events			AS NEEDED			
CAM62	Permanent Discontinuation of CAMUS Study Assessment (5)				Χ	Χ	X
CAM71	Jenkins Sleep Dysfunction Scale			X			Х
CAM72	Erectile Function			X			X
CAM73	Ejaculatory Function			X			Х
CAM74	Bladder Function		Х			Χ	X
CAM75	International Prostate Symptom Score	X	Х			Χ	X
CAM76	BPH Impact Index		Х			Χ	X
CAM77	Subjective Global Assessment						Х
CAM78	NIH-Chronic Prostatitis Symptom Index			Х			Х
CAM79	Participant Treatment Perception Form (4)						Χ
CAM81	Adverse Events				Χ	Х	Х

1. Assessment of all medications, including over-the-counter medications, every 12 weeks, plus every 4, 28, and 52 week and when an endpoint or adverse event occurs.

2. Screening Visit #2 and Baseline visit can be combined for participant's convenience.

3. Serum samples will be collected at Screening Visit #1 and the last scheduled visit.

4. Subject's guess at whether on active agent or placebo at 24, 48, 72 weeks.

5. Only complete if participant goes completely off study.
6. EKG can be taken at Screening Visit #1 or Screening Visit #2.
7. Visit 4, 28 and 52 can be either in office visit or via telephone interview.

8. Physical & DRE can be done at Screening Visit #1 or Screening Visit #2.

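### The protocol describes no remote way to collect the week-72 AUA score from a man who will not attend, because phone visits are offered only at weeks that do not carry the score

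*Combined protocol and SAP*

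**What the plan says.** **Remote visits.** Section 4.3 allows a choice of mode at three visits: "A participant has the option of either an office visit or phone interview for visits 4, 28 and 52". Note 7 of the Appendix I schedule agrees: "Visit 4, 28 and 52 can be either in office visit or via telephone interview". At these contacts forms are filled in over the phone: "All forms required at the visits will have to be completed during the interview".

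**The primary outcome.** Item 4.3.9 schedules the IPSS, which contains the AUA score, with the other "questionnaires, at the 12, 24, 36, 48, 60 and 72 week visits". The Appendix I row for the IPSS form matches. Sections 8.1 and 8.2.2 define the primary endpoint as the change in AUA score from baseline to week 72, compared by a two-group t-test. Section 4.4 makes the week-72 visit the last data collection for the primary and secondary analyses.

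**Follow-up and loss.** Section 5.9 states: "All participants should be followed for 72 weeks from the date of randomization, and should be encouraged to undergo all protocol procedures". Section 5.2 asks that men who stop study drug keep attending and that all their data other than pill counts be collected; it names no mode. Section 5.8 also encourages continued visits. Section 8.1 plans for loss: "To allow for a 10% dropout rate over the course of the study, 350 participants will be recruited to the study".

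**The concern.** The phone option and the AUA schedule do not overlap at any visit. Week 72 is also the most demanding follow-up visit: physical and rectal examination, blood tests, PSA, urinalysis, uroflow with residual volume, ECG, optional banked serum and the full set of questionnaires. A man who is unwilling to go through that has no stated way to give only the primary outcome, although it is a questionnaire and needs no equipment.

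A week-72 score that is not collected cannot enter the t-test, and section 8.2 gives no rule for replacing it. The repeated-measures model uses baseline and weeks 24, 48 and 72. A man absent only at week 72 therefore contributes scores from the first two dose levels and nothing from the third. An analysis method can only model the missing value, whereas a completed questionnaire supplies it.

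**Working it through.** **1. Visits side by side** (sections 4.3 and 4.3.9; Appendix I)

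| Follow-up visit (week) | Phone option | AUA score |
|---|---|---|
| 4, 28, 52 | yes | no |
| 12, 24, 36, 48, 60, 72 | no | yes |

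The other remote contacts in the protocol are adherence reminders by telephone or mail and contact about missed visits (section 5.3), and an optional mailed summary after database lock (section 4.4). None of them collects outcome data.

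**2. The plan's sample size.** Inputs from section 8.1: difference 2, SD 6, one-sided alpha 0.05, power 90%, 157 per arm, 10% dropout, 350 in total.

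- Normal approximation: n = 2(1.645 + 1.282)² × 6² / 2² = 154.1, so 155 per arm. The plan's 157 is within 2 of this.
- Noncentral t at 157 per arm: noncentrality 2 / (6√(2/157)) = 2.95 on 312 df, giving power 90.4%.
- Dropout: 314 / 0.90 = 348.9, so 349; the plan recruits 350, or 175 per arm.

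The plan's figures hold, and at the planned 10% loss the power target is met.

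**3. Power if some missing scores are recovered.** At 10% loss, 35 of 350 men have no week-72 score, or 17.5 per arm. ASSUMPTION: a third to a half of them would answer remotely.

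- A third recovered: 175 − 17.5 × 2/3 = 163.3 per arm, power 91.3%.
- Half recovered: 175 − 17.5 × 1/2 = 166.25 per arm, power 91.7%.

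If loss were heavier than planned, with half recovered (same kind of assumption):

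| Share with no week-72 score | Power, none recovered | Power, half recovered |
|---|---|---|
| 10% | 90.4% | 91.7% |
| 15% | 88.9% | 91.1% |
| 20% | 87.2% | 90.4% |

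**4. Room for bias.** With the same missing share m in both arms, an analysis of observed men is off by m × g, where g is the gap between the treatment effect in observed men and that in missing men. ASSUMPTION: g = 2 points, as large as the whole planned effect. A further assumption is that men still missing after recovery differ no more than those recovered.

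- No recovery: 0.10 × 2 = 0.20 points.
- A third recovered: 0.067 × 2 = 0.13 points.
- Half recovered: 0.05 × 2 = 0.10 points.

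For scale, the smallest observed difference that reaches significance at 157 per arm is 1.650 × 6√(2/157) = 1.12 points.

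**The case against.** The strongest reply is that asking for attendance is a sound choice. Weeks 4, 28 and 52 are light contacts, at week 4 and four weeks after each dose step, and suit a phone call. Week 72 needs the man present for most of its procedures, and a known phone fallback might reduce attendance and cost secondary and safety data. This stands, and it is why the remote route should be a last resort.

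Retention is also looked after elsewhere. Section 5.3 monitors visit adherence and follows up missed visits, section 10.4.4 sets up a committee that monitors retention, and sections 8.3.2 and 8.3.3 have the coordinating center track retention and overdue forms. The earlier one-year saw palmetto trial described in section 1.2 kept 97.5% of visits, so loss could be below 10%. That trial was shorter and used only the standard daily dose, so it does not settle the matter.

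A reader might infer three stronger things that the documents do not support:

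- **That men who stop capsules are lost.** Sections 5.2, 5.8 and 5.9 keep them in follow-up. Only the man who will not attend is left unaddressed.
- **That remote collection is forbidden, or that all remote contact is confined to three weeks.** The protocol is silent on remote collection at week 72, and section 5.3 allows other phone and mail contact. The Manual of Operations, which was not available for this review, may describe a route.
- **That missing men are known to differ by arm or by response.** No passage shows this.

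**Conclusion.** The point holds as an inexpensive improvement; it is not an error in the plan. Phone visits and AUA visits do not overlap, and the protocol gives no remote route for the score on which the primary test depends.

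It would be wrong to conclude that the trial is underpowered: the stated power holds with the planned 10% loss. The gain in power is about 1 percentage point, from 90.4% to between 91.3% and 91.7%, and it rests on the assumed recovery of a third to a half. It would be larger if loss exceeded the plan. The bias illustration, a reduction of 0.07 to 0.10 points, rests on an assumed 2-point gap and on unrecovered men being no more different than recovered ones. Both assumptions may be too favorable to the change, and the amount is small against 1.12 points. The main reason to act is that a missing week-72 score can be prevented only while the trial is running.

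**What to change.** In 4.3.9 and 5.9, add that when attempts to arrange the clinic visit have failed, and only then, the IPSS is collected at the scheduled time by mail for self-completion or, failing that, by phone, and that the mode is recorded.

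In 8.2.2, state that week-72 scores collected this way enter the primary t-test, and that any week-24 or week-48 scores so collected enter only the repeated-measures model, since the t-test does not use them. Repeat each analysis without the remote scores.

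The cost is protocol wording and a few mailings or calls by coordinators who already make such contacts. There are two small downsides. Phone answers may differ from self-completed ones; using mail first limits this and the repeat analysis would show its influence. Attendance may fall slightly, which the last-resort condition limits.
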